4.2 Study Overview

Study population: The study will be conducted in patients with early AD or early PD.

Dose selection: In Part 1 Posiphen will be tested at 80 mg QD and in Part 2, Posiphen will be tested at 5, 10, 20, 40 mg QD, for 25±2 days.

Whereas, the plasma t_{1/2} of Posiphen has been determined to be 5 hours, the CNS t_{1/2} has been measured to be over 12 hours, allowing that once daily dosing is feasible. Previous studies indicated that likely cholinergic adverse events are mostly driven by Cmax and occur at 160mg QD. Since our maximum dose is 80 mg QD, we do not expect any cholinomimetic effects.

Study Design: Part 1 is a study with 14 Early AD and 14 Early PD patients who are randomized to 80 mg of Posiphen or placebo. They will undergo a Screening Visit, and if they provide informed consent and are considered eligible per the inclusion and exclusion criteria, will proceed to participate in the treatment period. Period 1 consists of first-time dosing in clinic with administration of 80 mg of Posiphen or Placebo. Period 2 consists of an at home dosing period of 25±2 days, with daily administration of 80 mg of Posiphen or Placebo. Period 3 will be comprised of a stay at the clinical research unit where the subject will undergo study procedures that include safety assessments (AE and concomitant medication monitoring, 12-lead ECGs, clinical laboratory testing, vital signs assessments, and physical examinations), the last dose of Posiphen or Placebo, and 6 hours of PK blood and CSF sampling. At the end of blood/CSF sampling, the subjects will need to stay for a minimum of 1 hour of observation but may stay if necessary for observation until the following day (e.g., if the subject has blood/CSF sampling on Day 25, he/she may stay for observation until Day 26). After all end-of-study procedures are complete, the subject will be discharged to home. A 24-hour follow-up call will occur to assess the participants current condition and if there are any additional adverse events to report.

After completion of Part 1 of the study, the plasma and CSF samples will be analyzed for the biomarkers to determine if changes are needed to the biomarkers to be measured in Part 2. Since the conduct of the study in Part 2 will be identical to the conduct of the study in Part 1, recruitment will continue uninterrupted. The only potential change between Part 1 and Part 2 are the biomarkers to be measured.

Part 2 is a study with 40 Early PD patients, 10 patients each who are randomized to one of 4 treatment conditions of Posiphen (5 mg, 10 mg, 20 mg, or 40 mg). They will undergo a Screening Visit, and if they provide informed consent and are considered eligible per the inclusion and exclusion criteria, will proceed to participate in the treatment period. Period 1 consists of first-time dosing in clinic with administration of 5, 10, 20, or 40mg of Posiphen. Period 2 consists of an at home dosing period of 25±2 days, with daily administration of 5, 10, 20, or 40mg of Posiphen. Period 3 will be comprised of a stay at the clinical research unit where the subject will undergo study procedures that include safety assessments (AE and concomitant medication monitoring, 12-lead ECGs, clinical laboratory testing, vital signs assessments, and physical examinations), the last dose of Posiphen or Placebo, and 6 hours of PK blood and CSF

sampling. At the end of blood/CSF sampling, the subject will need to stay for a minimum of 1 hour of observation but may stay if necessary for observation until the following day (e.g., if the subject has blood/CSF sampling on Day 25, he/she may stay for observation until Day 26). After all end-of-study procedures are complete, the subject will be discharged to home. A 24-hour follow-up call will occur to assess the participant's current condition and if there are any additional adverse events to report.

For both parts, subjects who drop out during the initial 3-week at home treatment period will be discontinued and replaced by new subjects. If 4 subjects are discontinued due to adverse events a safety review will be conducted.

Outcome measures to assess pharmacodynamics: Translational inhibition of the aSYN mRNA will result in decreased production of aSYN, which may be reflected by decreased secretion of the aSYN monomers and oligomers into the spinal fluid. Similarly, translational inhibition of the APP mRNA will result in decreased production of APP and its fragments, which may be reflected by decreased secretion of the A β monomers and oligomers into the spinal fluid. We also will measure secreted sAPP α and sAPP β and levels of tau and p-tau in CSF. sAPP reflects processing of APP by α -secretase to produce sAPP α and β -secretase (BACE) to produce sAPP β . Tau levels are being measured since we found that tau translation may be under the regulation of a similar iron-responsible element (IRE) that may also be affected by Posiphen treatment. In fact, we have measured in human CSF and in mouse brain that tau and p-tau levels are lowered by Posiphen treatment.

Safety outcome measures: Reports of adverse events (AEs) and serious adverse events (SAEs) during exposure to Posiphen will be collected to evaluate if there are any significant clinical safety issues for the study population. All SAEs occurring up to 30 days after last study drug administration that are considered drug-related must also be reported. Extensive clinical and laboratory safety data already exist for Posiphen; therefore, this approach will be sufficient in the proposed study.

Clinical, functional and cognitive assessment measures: Although clinical benefit is unlikely due to the short duration of this study, AD and PD specific tests will be performed. It is predicted that cognition and function will remain stable over the course of drug exposure; however, this will be assessed formally in the clinic. For both populations, the MMSE ([Folstein 1975](#)) will be administered as a global measure of cognition and the Coding subtest from the Weschler Adult Intelligence Scales, 4th edition (WAIS-IV) will serve as a sensitive measure of CNS dysfunction. The subjects with AD will also be administered the ADAS-Cog 14 ([Schafer 2012](#)). The subjects with PD will be administered the [Hoehn & Yahr \(1967\)](#) for determination of inclusion into the study. Functional impairment will be evaluated using the Clinical Dementia Rating (CDR) scale ([Berg1988](#)) for AD and the MDS-UPDRS ([Goetz 2008](#)) for those with PD.

5 POTENTIAL RISKS AND BENEFITS OF INVESTIGATIONAL PRODUCT AND STUDY PROCEDURES**5.1 Risks and Benefits Associated with Posiphen or Placebo**

There are no benefits to the subjects other than receiving medical and selective functional and cognitive evaluations.

The clinical investigator must advise all potential subjects of the possibility of unexpected side effects and carefully evaluate each person exposed to Investigational Product for possible AEs.

Side effects to the Placebo are not uncommon but are obviously not due to a pharmacological agent as an industry standard placebo (non-lactose compound) will be provided. The placebo used for the study consists of microcrystalline cellulose which is generally recognized as safe (GRAS), with no known side effects anticipated.

In clinical studies to date, Posiphen has been well tolerated with single doses of 80 mg or less and QID doses of 60 mg up to 25 days. A higher single dose of 160 mg was associated with an increased incidence of nausea and vomiting, potentially cholinergic based side effects, which resulted in the decision not to test higher single doses. Aside from nausea and vomiting, which are well-known responses to treatment with ChE inhibitors, the only consistent pattern of AEs entailed dizziness/fainting, headache, and reduction in total serum protein. These effects were seen to varying degrees at all doses of Posiphen and also in the Placebo group. There was a tendency, but no definitive pattern of increased incidence of AEs with increasing dose of Posiphen. There have been no SAEs in prior clinical studies with Posiphen.

Definitive reproductive and developmental toxicity studies have not been conducted with Posiphen. As a result, women of childbearing potential will be excluded from participating in this study.

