DURATION OF STUDY PARTICIPATION	Each subject will have up to a 42-day screening period, a baseline visit including a lumbar puncture (LP), followed by 25±2 days of treatment at home, followed by an in clinic visit that includes treatment and a 6-hour LP procedure.
SUMMARY OF INVESTIGATIONAL PRODUCT	
Part 1: Posiphen/placebo 80 mg QD, taken orally for 25±2 days by Early AD and PD patients.
 
Part 2: Posiphen at 5, 10, 20, or 40 mg QD, taken orally for 25±2 days by Early PD patients.

SUMMARY OF KEY ELIGIBILITY CRITERIA: FOR AD	
 • Diagnosis of early AD • Age 45 or older • MMSE 18-28 • Clinical Dementia Rating (CDR) of 0.5 or 1.0
SUMMARY OF KEY ELIGIBILITY CRITERIA: FOR PD	
 • Diagnosis of early PD • Age 45 or older • MMSE 18-30 • Hoehn & Yahr ≤ 4
PRIMARY OUTCOME MEASURES	
Aim 1. Safety and Tolerability
 
Aim 2. PK of Posiphen in Plasma

EXPLORATORY MEASURES	
TARGET ENGAGEMENT
 
Levels of neurotoxic proteins in blood, plasma and CSF:
 
 • aSYN and Aβ monomers and dimers, and infective oligomers • Aβ38, Aβ40, Aβ42 • soluble Amyloid Precursor Proteins: sAPPα and sAPPβ • T-Tau and P-Tau proteins 
PATHWAY ENGAGEMENT
 
Levels of proteins involved in the toxic cascade leading to nerve cell death in blood, plasma and CSF

	
• Neurotransmitters• Neurotrophic factors• Inflammatory factors• Synaptic factors• Control proteins that should not change 
FUNCTIONAL/COGNITIVE MEASURES
 
PD: MMSE, WAIS-IV, MDS-UPDRS
 
AD: MMSE, WAIS-IV, ADAS-Cog 14, CDR

--	--

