6.3 Safety and Tolerability Analysis

Safety and tolerability will be assessed with physical examinations, vital signs, clinical laboratory values, 12-lead ECG, use of concomitant medications, and AE reports. The frequencies of adverse events, serious adverse events and laboratory abnormalities between the participants across the treatment groups will be compared. The severity of cholinergic adverse events will be carefully evaluated taking the criteria in [Appendix 2](#) into consideration (modified from the latest version of the Common Terminology Criteria for Adverse Events (CTCAE)) as there is potential for an interaction between Posiphen and Donepezil through the inhibition of AChE, thereby resulting in increased cholinergic activity.

Subjects who dropout during the initial 3-week at-home treatment period will be discontinued and replaced by new subjects. If 4 subjects are discontinued due to adverse events a safety review will be conducted.

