14.1 Definition

An AE is defined as per the US Code of Federal Regulation, Title 21, Part 312.32 [<http://www.accessdata.fda.gov/scripts/cdrh/cfdocs/cfcfr/cfrsearch.cfm?fr=312.32>]. An AE is any untoward medical occurrence associated with the use of a drug in humans, whether or not considered drug related.

Collection of adverse events will begin once informed consent is signed and will continue until the follow-up phone call performed on the day after discharge. Adverse events include but are not limited to: (1) worsening or change in nature, severity, or frequency of conditions or symptoms present at the start of the study; (2) Subject deterioration due to primary illness; (3) intercurrent illness; and (4) drug interaction. An abnormal laboratory value will only be reported as an AE if the investigator considers it clinically significant, or if it leads to the Subject being withdrawn from the study.

The investigator should attempt to establish a diagnosis of the event based on signs, symptoms, and or other clinical information. In such cases, the diagnosis should be documented as the AE and not the individual signs or symptoms. Symptoms and conditions present at the beginning of the study will be characterized, so that AEs can be defined as any new symptom, or any increase in frequency or severity of an existing symptom. Adverse events should be described with medical terminology so that the event can be matched against a medical coding dictionary, such as MedDRA (Medical Dictionary for Regulatory Activities).

Investigators should report their assessment of the potential relatedness of each AE to the protocol procedure, and to the investigational product, and/or drug delivery system used in the protocol.

Following questioning and evaluation, all AEs, whether determined to be related or unrelated to the study drug by a medically qualified site PI or clinician must be documented in the Subject's records, in accordance with the investigator's normal clinical practice, and on the AE electronic case report form (eCRF).

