15.2 Reporting SAEs

Collection of serious adverse events will begin once informed consent is signed (regardless of study drug exposure) and will continue until 30 days following the last dose of study drug. All SAEs must be reported to the Medical Monitor, the Sponsor, Project Directors and the Coordinating Center within 24 hours of learning of the event. This in turn will trigger an alert to

the appropriate Coordinating Center personnel and Protocol Project Directors, which will lead to the initiation of the creation of the report. A notification will be sent to all participating sites and the DSMB once the report is available. Sites will inform their IRB of the event based on local IRB requirements. The Sponsor is the IND holder and is responsible for submitting any SAEs according to the FDA reporting requirements.

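### Protocol section 4.2 limits post-treatment SAE reporting to drug-related events, contrary to section 15.2, which collects all SAEs to 30 days after the last dose

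*Protocol*

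**What the plan says.** Section 4.2 of the protocol, under the safety outcome measures, states that "Reports of adverse events (AEs) and serious adverse events (SAEs) during exposure to Posiphen will be collected". For the time after treatment it adds: "All SAEs occurring up to 30 days after last study drug administration that are considered drug-related must also be reported". It then justifies this as sufficient, on the ground that extensive safety data already exist.

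Section 15.2 starts SAE collection at informed consent, whether or not study drug has been taken, and says that it "will continue until 30 days following the last dose of study drug". On scope it is unconditional: "All SAEs must be reported to the Medical Monitor, the Sponsor, Project Directors and the Coordinating Center within 24 hours" of learning of the event.

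Section 14.1 sets the period for adverse events in general. Collection starts at consent and "will continue until the follow-up phone call performed on the day after discharge". Events are documented whether or not they are judged related to study drug, and relatedness is assessed separately for the protocol procedure and for the product.

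The synopsis lists "Aim 1. Safety and Tolerability" among the primary outcome measures, and section 6.3 says: "The frequencies of adverse events, serious adverse events and laboratory abnormalities between the participants across the treatment groups will be compared".

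SAP section 7.3.1 counts SAEs and procedure-related events in the overview (Table 14.4.1.1) and tabulates SAEs by cohort and treatment group (Table 14.4.1.6). SAP section 5.3 defines treatment-emergent events as starting or worsening on or after the first dose, with no end date. It refers to dosing and follow-up periods without defining follow-up.

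**The concern.** The two protocol sections give different answers to a simple question: must an SAE in the month after the last dose be reported if the investigator thinks the drug did not cause it? Section 15.2 says yes. Section 4.2 asks only for events attributed to the drug.

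A causality filter at the reporting stage cannot be undone at analysis, because an event that never reaches the database cannot be tabulated or reassessed. The events most plainly exposed are procedural. Section 9.4.2 has the CSF catheter placed at the confinement visit, the final dose given after the hour-0 sample, and sampling continued for six hours. Section 5.3 lists meningitis, infection, epidural or subdural bleeding, paralysis and nerve-root injury among the risks of CSF sampling. A serious event of that kind could reasonably be judged related to the procedure and not to the drug. The SAP overview table means to count it; section 4.2 would not require it.

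**Working it through.** No figure in the plan is at issue, so the check is a comparison of the rules. The table takes an SAE in each period and asks whether each section requires it. Section 4.2 does not define exposure; it is taken here to end with the last dose.

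| SAE timing and attribution | Section 4.2 | Section 14.1 (as an AE) | Section 15.2 |
|---|---|---|---|
| After consent, before first dose | Not mentioned | Yes | Yes |
| During treatment, any cause | Yes | Yes | Yes |
| After last dose, up to the follow-up call, not drug-related | Not required | Yes | Yes |
| After the call, within 30 days of last dose, drug-related | Yes | Collection ended | Yes |
| After the call, within 30 days of last dose, not drug-related | **Not required** | **Collection ended** | **Yes** |

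Reading down the rows:

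1. In the first and third rows section 4.2 is narrower than section 15.2, but section 14.1 independently collects the event as an adverse event. Loss from the database is unlikely there.
2. In the second and fourth rows sections 4.2 and 15.2 agree.
3. In the last row section 15.2 alone secures the event. Section 14.1 has stopped, and section 4.2 does not ask for an event that is unrelated to the drug or related only to the procedure.

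Next, whether another provision settles the last row:

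- **Precedence.** Neither document says that section 15.2 overrides section 4.2.
- **Wording.** Section 4.2 does not read as a loose summary. It states a rule and defends it as adequate.
- **SAP.** Sections 5.3 and 7.3.1 apply no relatedness filter to SAEs and set no end to the window. The SAP therefore reports whatever was collected and does not say what should have been.

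The conflict is therefore real. Its practical reach is SAEs not attributed to drug, occurring after the follow-up call and within 30 days of the last dose.

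**The case against.** The strongest reply is that the operative section is clear. Section 15.2 is headed as the SAE reporting section and gives start, stop, scope, recipients and a 24-hour clock. Section 4.2 is an overview. It says that certain SAEs must also be reported, and it does not forbid reporting others. A site that complies with section 15.2 complies with both; a site that reports only related events breaches section 15.2. This stands, and it is the main reason to expect a small effect. It does not make the rule in section 4.2 correct: that section states a narrower requirement than the one the protocol imposes elsewhere.

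It can also be said that few SAEs are expected. Section 5.1 reports none in prior clinical studies, and section 2 reports none attributed to Posiphen in the ongoing study. This stands too.

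The catheter example has limits. No passage says that such complications appear late, and section 14.2 requires events already identified to be followed until they subside or stabilise. The catheter procedure is also common to drug and placebo patients. The example shows how an SAE could go unreported; it does not show distortion between groups.

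A reader might go further and infer that a primary safety count depends on which section a site follows. The documents define no such count. Safety and tolerability is an aim assessed through adverse events, examinations, vital signs, ECGs and laboratory values, and only the SAE summaries are touched.

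**Conclusion.** Section 4.2 is wrong as written against the protocol's own SAE reporting section, and the passages must be reconciled. The consequence is possible under-reporting of SAEs not attributed to drug, mainly after the follow-up call, with a corresponding gap in SAP Tables 14.4.1.1 and 14.4.1.6.

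The likely impact is small and cannot be quantified, because the documents give no SAE rate. Two inferences would overstate it. One is to cite how far a single event shifts the proportion in a group of ten or four: that is true of any event in a group of that size and says nothing about how often this discrepancy would matter. The other is to cite the time without scheduled contact after the follow-up call: that is the same under either section and so does not measure the conflict.

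The conclusion assumes that exposure in section 4.2 ends with the last dose and that a site might take section 4.2 as its rule. Neither assumption is needed to establish that the two texts disagree.

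**What to change.** In protocol section 4.2, delete the clause that limits post-treatment SAE reporting to drug-related events, and replace the description of collection during exposure with the SAE period in section 15.2: all SAEs, from consent to 30 days after the last dose. A cross-reference to section 15.2 would do the same job.

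In SAP section 7.3.1, state that the SAE summary in Table 14.4.1.6 covers that window with no relatedness filter. SAEs starting before the first dose remain identifiable through the SAP's existing pre-treatment definition.

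The cost is about one sentence in each document. The edit aligns section 4.2 with what section 15.2 already requires and adds no visit, contact or procedure.

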5.2 Risk/Benefit Associated with Blood Collections

Phlebotomy is associated with mild to moderate discomfort due to piercing of the skin. This can be minimized with the use of a well-trained phlebotomist/nurse. Sometimes the blood draw site may become discolored with a “bruised” appearance that is transient and not painful. Rarely, the blood draw site may become infected and require antibiotic treatment.

5.3 Risk/Benefit Associated with CSF Sampling

The most frequent adverse event associated with these studies was post-lumbar puncture headache. This was successfully managed by blood patching if a participant is unresponsive to orally administered fluids and/or caffeine.

Other potential risks include meningitis, pain or tingling sensation in the lower extremities, temporary eye weakness or double vision, infection or bleeding at the site of catheter insertion,

pain at the site of insertion, backache, epidural or subdural bleeding, infection, paralysis and potential injury to the nerve root.

6 SAMPLE SIZE AND STATISTICAL PLAN

For Part 1: A sample size of up to 2x14 subjects (10 randomized to Posiphen and 4 to Placebo for AD and PD respectively) is planned.

For Part 2: A sample size of up to 40 Early PD patients is planned to be randomized to Posiphen, 10 patients each dosed at 5 mg, 10 mg, 20 mg, or 40 mg.

Definitions of the analysis populations and a detailed description of the analysis rules will be presented in a separate Statistical Analysis Plan (SAP).

6.1 Randomization

Subjects who have signed an informed consent and meet screening eligibility requirements will be randomly assigned to the active and placebo treatment groups (10 randomized to Posiphen and 4 to Placebo for AD and PD, respectively) in Part 1. In Part 2, 40 Early PD patients will be randomly assigned, 10 patients each to one of the 4 different dose levels of Posiphen (5, 10, 20 or 40mg).

6.2 Power and Sample Size Determination

This is an exploratory study to assess safety, tolerability and pharmacokinetics for Early AD and Early PD patients in addition to investigating pharmacodynamics and efficacy focusing on target engagement, pathway engagement and functional/cognitive measures. 10 patients per dose group provides enough data to characterize the PK of Posiphen as well as adequately supporting potential dose proportionality analyses.

Due to the sample size computation below, we will state that sAPP α , sAPP β and aSYN were given specific consideration in deciding the need to have 10 Posiphen patients in each treatment group given their specific importance in the emergence and progression of AD and PD. The statistical background and rational for having 10 Posiphen patients in each treatment group to have a meaningful interpretation of sAPP α , sAPP β and aSYN data are outlined below.

The statistical evaluation of our previous study in MCI patients with soluble APP α and β levels measured in spinal fluid before and after Posiphen administration (Protocol QR12001) can be used to power this study ([name] 2012). All assay data collected were analyzed using a repeated measure mixed model analysis of variance. The model included Day (Day 11/Day0) as a fixed effect, Time (9 time points per person between 0 and 6 hours) as a repeat measure effect

and Patient (18 samples per person total) as a random effect. Data are presented as means \pm SEs. The statistical evaluations were undertaken by Data Magik (Salisbury, UK).

Human biomarker	CSF % of time 0	SE	p Value
(A) AD biomarkers			
sAPP α	-59.9%	0.231	0.0006
	-34.1%	0.659	0.0661
sAPP β	-57.7%	0.361	0.0001
	-34.0%	1.516	0.0901

Analysis of sAPP α and β using type, day and id as variables shows:

	type	time	N	delta_MN	delta_SE	delta_SD	%chng_MN	%chng_SE	z	pv
1	alpha	1.5h	4.0000	0.0603	0.0960	0.1921	0.0561	0.2167	0.6273	0.5304
2	alpha	2h	4.0000	0.1245	0.0423	0.0846	0.3020	0.0690	2.9445	0.0032
3	alpha	6h	3.0000	0.2660	0.0558	0.0967	0.4542	0.1367	4.7650	0.0000
4	alpha	8h	4.0000	0.3135	0.0847	0.1695	0.5248	0.0653	3.6995	0.0002
5	alpha	0h	4.0000	0.0948	0.0928	0.1856	0.1691	0.2493	1.0213	0.3071
6	alpha	12h	4.0000	0.2960	0.0623	0.1245	0.4966	0.0862	4.7549	0.0000
7	alpha	1h	4.0000	-0.0683	0.1660	0.3320	-0.4285	0.6604	-0.4111	0.6810
8	alpha	3h	4.0000	0.4858	0.3922	0.7844	0.3579	0.1981	1.2385	0.2155
9	alpha	4h	4.0000	0.3030	0.2753	0.5505	0.3200	0.2905	1.1008	0.2710
10	beta	1.5h	4.0000	-0.1160	0.2670	0.5339	-0.7568	0.9151	-0.4345	0.6639
11	beta	2h	4.0000	0.1975	0.0876	0.1752	0.3639	0.1315	2.2550	0.0241
12	beta	6h	3.0000	0.4717	0.0572	0.0991	0.5910	0.0519	8.2431	0.0000
13	beta	8h	4.0000	0.5715	0.1271	0.2542	0.6648	0.0550	4.4960	0.0000
14	beta	0h	4.0000	0.1092	0.1134	0.2268	0.1425	0.2227	0.9632	0.3354
15	beta	12h	4.0000	0.4620	0.0581	0.1161	0.6040	0.0604	7.9570	0.0000
16	beta	1h	4.0000	-0.4895	0.1652	0.3304	-1.4024	0.6361	-2.9635	0.0030
17	beta	3h	4.0000	2.2147	1.9988	3.9977	0.5025	0.1616	1.1080	0.2679
18	beta	4h	4.0000	0.0277	0.3313	0.6626	-0.2181	0.2404	0.0838	0.9332

The results of the 10 days at 8 hours on sAPP α and β is SD = 0.1695.

Assuming type one error, $\alpha=0.05$ and type two error, $\beta=0.2$, or a power of 0.8, the calculated sample range of delta effect sizes was 0.3 to 2 SD.

	delta	standardized_delta	N
1	0.08	0.30	175.00
2	0.10	0.40	99.00
3	0.13	0.50	64.00
4	0.15	0.60	45.00
5	0.18	0.70	39.00
6	0.20	0.80	26.00
7	0.23	0.90	20.00
8	0.25	1.00	17.00
9	0.28	1.10	14.00
10	0.31	1.20	12.00
11	0.33	1.30	10.00
12	0.36	1.40	9.00
13	0.38	1.50	8.00
14	0.41	1.60	7.00
15	0.43	1.70	7.00
16	0.46	1.80	6.00
17	0.48	1.90	5.00
18	0.51	2.00	5.00

sAPP α

Using the above data, we can calculate that a power analysis of APP α shows the requirement of 9 people to see a 36% change in sAPP α levels at a statistical significance level of >0.05

delta	standardized_delta	N
1	0.05	175.00
2	0.07	99.00
3	0.08	64.00
4	0.10	45.00
5	0.12	33.00
6	0.14	26.00
7	0.15	20.00
8	0.17	17.00
9	0.19	14.00
10	0.20	12.00
11	0.22	10.00
12	0.24	9.00
13	0.25	8.00
14	0.27	7.00
15	0.29	7.00
16	0.31	6.00
17	0.32	5.00
18	0.34	5.00

sAPP β

Using the above data, we can calculate that a power analysis of APP β shows the requirement of 9 people to see a 24% change in sAPP β levels at a statistical significance level of >0.05 . We are expecting changes in sAPP α and β levels to be between 20 and 50% and for the higher doses an $n < 5$ would be adequate to detect those changes.

aSYN

However, we do not expect the changes in alpha-synuclein and in neurotransmitters to be that pronounced. Therefore, we chose an $n=10$. If dropouts are to occur, they will be replaced to allow the full sample size of 5×10 participants to be achieved.

